7.0 Setting

1. The TMS treatment will be completed at Brain Stimulation Division in the Department of Psychiatry.
2. Screening and follow-up will be completed at Hollings Cancer Center (HCC).

Study Site

A single study site is at the Medical University of South Carolina.

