10.2 Baseline Evaluation

After the informed consent is obtained, participants will be assessed for study inclusion/exclusion criteria.

(1) Demographic Data: Basic demographic information including age, gender, race, and medical history will be collected. (2) Mini International Neuropsychiatric Interview (MINI) (32): This is a well-standardized structured instrument used to provide quick and accurate DSM-IV psychiatric diagnoses. The MINI will be used to confirm the inclusionary/exclusionary diagnoses in the participants. (3) Tobacco Use History: Detailed history of current and past tobacco use will be obtained, including cigarette smoking. The questions addressed will include the amount, frequency, duration of smoking, preferred brand, reasons for smoking, smokeless tobacco, family history, etc. (4) Fagerstrom Test for Nicotine Dependence (FTND)(33): This is a self-rating questionnaire for nicotine dependence. (5) Questionnaire of Smoking Urges- Brief (QSU-B) (34): This is a 10-item self-rating questionnaire for assessment of craving. (6) Minnesota Withdrawal Scale - Revised (MNWS-R) (35): MNWS-R is a DSM-IV based instrument to assess symptoms of nicotine withdrawal. (7) Biomarkers: We will also use carbon monoxide (CO) level in the expired air by a standard CO breathalyzer at each visit. (8) Tobacco diary: This is a daily diary of all tobacco products consumed in the period between visits,

including cigarettes. Participants will maintain a daily tobacco diary, which will be collected at each visit.

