10.5 Study Calendar

Timepoints	Baseline	TMS 1	TMS 2	TMS 3	TMS 4	TMS 5	Follow-up
Assessments							
Informed Consent	X						
Demographic	X						
Medical history	X						
Tobacco Use History	X						
Fagerstrom Test for Nicotine Dependence (FTND)	X						
Questionnaire of Smoking Urges- Brief (QSU-B)	X						

Minnesota Withdrawal Scale - Revised (MNWS-R)	X						
carbon monoxide (CO)	X						
Tobacco diary	X						
Primary Outcome – number of abstinence days	X	X	X	X	X	X	
Secondary Outcome – cigarette per day	X	X	X	X	X	X	
Visual analog scale of craving for cigarette	X	Pre and post X					
Adverse Events		X	X	X	X	X	
Best guess		X				X	
Phone call							X

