12.0 Data Management

12.1. Data collection

Data analyses will include the use of descriptive statistics for feasibility metrics and outcome measures. Graphical displays will be used to illustrate the effect of rTMS vs. sham TMS on the outcomes over time. General linear mixed models, ideal for modeling repeated longitudinal outcome data, will be used to estimate the potential treatment benefit of rTMS on numbers of cigarettes smoked per day. Poisson (or negative binomial) regression models will be used to estimate the potential treatment benefit of rTMS on numbers of days abstinent from cigarette smoking during their 7-days following their quit attempt. The regression models will allow us to estimate rTMS treatment benefit along with 95% confidence intervals. All analyses will be conducted in collaboration with the SCTR BERD biostatisticians.

The data from follow-up will be used to measure the durability of one week rTMS treatments. We hypothesized that the number of quit day would predict a long-term effect for smoking cessation.

Electronic and hard copy CRF's will be provided for the recording of data. With the exception of hard copy case report forms utilized for expedited reporting requirements, such as the reporting of SAE's, the remainder of patient data will be collected and submitted via electronic CRFs. All data should be substantiated by clinical source documents organized within a patient research record. ICH Good Clinical Practices are to be followed.

Electronic data for on study and follow-up patient data is submitted via REDCap. REDCap is managed from the Medical University of South Carolina as a consortium partner under their CTSA. REDCap CRF is a secure, Web-based application designed to capture and manage research study data.

The system has been reviewed for 21CFR Part 11 compliance and has been deemed "21CFR 11 Capable." Users of the REDCap system are limited to members of the IRB approved research team

who are delegated data management responsibilities, typically the study coordinator and data manager.

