12.2 Data analysis

General considerations: All data will be analyzed in consultation ([name]) with the electronic system called REDCap (Research Electronic Data Capture). Statistical analyses will be performed using SPSS 22.0 (IBM Inc.). Baseline demographic and baseline characteristics, together with safety analyses will be performed on all enrolled subjects. Baseline values are defined as the measures on screening visit. The standard summary statistics for continuous variables are: mean, standard deviation, median, minimum and maximum. The standard summary statistics for categorical variables are: count and percentage. All statistical tests will be two-sided. For comparison of means (continuous variables), the two-sample t-test or the Wilcoxon rank sum test will be used as appropriate. For comparison of proportions (discrete data), the Chi-squared test will be used as appropriate. All test performed at significance $\alpha = 0.05$.

To assess a feasibility of the rTMS for smoking cessation in cancer patients: The numbers of subjects who were randomized and who entered and completed each visit of the study will be provided, as well as the reasons for all post-randomization discontinuations, grouped by treatment and by major reason. The discontinued subjects, protocol deviations, and subjects excluded will be provided as well.

To obtain the secondary estimates: The abstinence days, and cigarette consumption and cue-elicited craving will be compared between the active TMS and sham groups with a t-test or a repeated measures analysis of covariance model. Baseline daily number of cigarettes smoked, sex and center will be used as covariates.

To analyze the exploratory measures: cue-induced craving (QSU – Brief) and visual analog scale for craving will be measured pre and post each rTMS session. Other assessment, Carbon Monoxide, FTND, and MNWS-R will be compared between two groups.

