13.0 Provisions to Monitor the Data to Ensure the Safety of Subjects

1. *Trial Management:* The study will be managed from the Brain Stimulation Lab within the Department of Psychiatry and Behavioral Sciences at the Medical University of South Carolina.
2. *Data Management and Analysis:* Data will be entered by research assistants directly into a computer using standard database software. The data analysis plan is outlined in the Data Analysis Plan section.
3. *Quality Assurance:* The PI will have weekly meetings with the research assistants to discuss qualitative comments received during data collection and any problems in data collection. The statistician will periodically examine the database to look for irregularities. Initial data analyses will examine distributions of variable scores, and comparability of baseline characteristics across conditions in case analyses need to be adjusted for these. Confidentiality protections are outlined above.
4. *Regulatory Issues:* All unexpected Adverse Events (AEs) will be reported to the MUSC IRB and Committee on Human Research within 48-business hours. Serious AEs will be reported within 24-business hours. Follow-up of all unexpected and serious AEs will also be reported to these agencies.

5. *Definition of AE and SAE:* An AE is defined as any untoward medical occurrence in a study subject administered a pharmaceutical product that does not necessarily have a causal relationship with this treatment (ICH GCP). Any unwanted change, physically, psychologically or behaviorally, that occurs in a study participant during the course of the trial is an adverse event. A Serious Adverse Event (SAE) is defined as an adverse event that has one of the following outcomes: death, life-threatening, inpatient hospitalization or prolongation of existing hospitalization, persistent or significant disability/incapacity, a congenital anomaly/birth defect.

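### Section 12.2 does not list baseline craving as a covariate for cue-elicited craving, nor say how a pre-treatment value enters; prespecifying it could sharpen a preliminary estimate at little cost

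*Combined protocol and SAP*

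**What the plan says.** Section 12.2 (Data analysis) treats abstinence days, cigarette consumption and cue-elicited craving together. They are compared between arms "with a t-test or a repeated measures analysis of covariance model", and one covariate list serves all three: "Baseline daily number of cigarettes smoked, sex and center will be used as covariates". The list contains the baseline of one of these outcomes (cigarettes) but not of craving. The same section says "Baseline values are defined as the measures on screening visit".

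Craving is measured before treatment. Section 10.2 includes the QSU-B in the baseline evaluation ("This is a 10-item self-rating questionnaire for assessment of craving"). The calendar in section 10.5 marks both the QSU-B and the "Visual analog scale of craving for cigarette" (VAS) at Baseline, and the VAS again before and after the TMS sessions.

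No other section supplies the missing rule:

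- Section 12.1 names general linear mixed models, which "will be used to estimate the potential treatment benefit of rTMS on numbers of cigarettes smoked per day", and Poisson or negative binomial regression for days abstinent. It names no model for craving.
- Section 13.0 (Quality Assurance) has initial analyses look at "comparability of baseline characteristics across conditions in case analyses need to be adjusted for these". It names no covariate and no criterion.
- Section 12.3 mentions change from baseline, but only for safety.

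**The concern.** The craving comparison belongs to the objective of obtaining preliminary estimates (section 1.2), so the width of its confidence interval is most of what it has to offer. With 20 patients, the arms can easily differ by chance in baseline craving. If baseline craving predicts later craving, an analysis of post-treatment values that ignores it carries part of that difference into the estimate, and its interval is wider than the collected data require.

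The open choices add to this. Section 12.2 gives no rule for choosing between the t-test and the ANCOVA, and section 13.0 leaves adjustment to be decided after looking at baseline balance. Settling the model in advance removes that freedom.

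**Working it through.** **Inputs.** From the documents: N = 20 (sections 6.0 and 10.1), two-sided tests at 0.05 (section 12.2), one site (section 7.0). Assumed: 10 per arm (no allocation ratio is given), one post-treatment craving value with SD 1, equal variance at baseline, and cigarettes and sex explaining nothing. The correlation r between baseline and post-treatment craving is not given, so a range is shown. The plan has no power or precision figure for craving to reproduce.

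**Formula.** With k covariates besides treatment, half-width = t(0.975, 18-k) × sqrt[0.2 × (1-R²) × 17/(17-k)]. Here 0.2 = 2/10, and the last factor, the cost of chance imbalance, is 1 when k = 0.

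- t-test on post-treatment values (k = 0): 2.101 × sqrt(0.2) = 0.940 SD.
- Baseline craving alone (k = 1): 2.110 × sqrt(0.2 × 17/16) = 0.973 SD at r = 0, then multiplied by sqrt(1-r²).
- Planned ANCOVA on cigarettes and sex (k = 2; center is constant): 2.120 × sqrt(0.2 × 17/15) = 1.009 SD.
- Baseline craving added to that ANCOVA (k = 3): 2.131 × sqrt(0.2 × 17/14) = 1.050 SD at r = 0.
- t-test on change: 0.940 × sqrt[2(1-r)].

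| r | Craving alone | v post-value t-test (0.940) | Added to ANCOVA | v ANCOVA (1.009) | Change-score t-test | Craving alone v change |
|---|---|---|---|---|---|---|
| 0 | 0.973 | +3.5% | 1.050 | +4% | 1.329 | -27% |
| 0.3 | 0.928 | -1% | 1.002 | -1% | 1.112 | -17% |
| 0.5 | 0.842 | -10% | 0.910 | -10% | 0.940 | -10% |
| 0.7 | 0.695 | -26% | 0.750 | -26% | 0.728 | -5% |

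**Break-even.** Against the post-value t-test: r = sqrt[1 - (0.9396/0.9726)²] = 0.26. Added to the planned ANCOVA: r = sqrt[1 - (1.0093/1.0504)²] = 0.28. With 8 completers per arm these become 0.30 and 0.33. If all three covariates are used and compared with the post-value t-test, the break-even is sqrt[1 - (0.9396/1.0504)²] = 0.45, because cigarettes and sex use two further degrees of freedom.

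**Chance imbalance.** The baseline gap has SD sqrt(0.2) = 0.447, and 0.5/0.447 = 1.118. So P(|gap| > 0.5 SD) = 2 × [1 - Φ(1.118)] = 0.26. The mean gap in those trials is 0.447 × φ(1.118)/[1 - Φ(1.118)] = 0.725 SD.

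- Post-value analysis: shift of r × 0.725 = 0.22, 0.36, 0.51 SD at r = 0.3, 0.5, 0.7.
- Change score: shift the other way of (1-r) × 0.725 = 0.51, 0.36, 0.22 SD.
- With baseline craving as covariate: about 0. A simulation of 20,000 trials per r agreed, with a mean shift below 0.01 SD.

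**The case against.** The strongest reply is that this is silence in the plan, not a demonstrated error. A reader might infer that neither planned analysis uses baseline craving. The documents do not support that. Sections 1.3, 4.3 and 12.2 have craving measured before and after each session, so a t-test on change or a group-by-time contrast is a possible reading, and either would use pre-treatment craving. This stands: the finding has to be that section 12.2 does not say how baseline craving enters, and the size has to be given under both readings. Against a change score the gain at r = 0.7 is about 5%, not 26%.

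A reader might also take the shifts of 0.22 to 0.51 SD as bias in whatever analysis is run. They are not. They apply to a post-value analysis, in the roughly 26% of randomisations with a gap above 0.5 SD, and they are chance error that the confidence interval already reflects.

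The gain is also uncertain. The quit attempt starts after the first TMS session (section 10.4), so screening craving precedes it and later craving falls within it. Nothing in the documents shows that r is moderate. This stands as a limit on size.

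Finally, section 13.0 partly anticipates adjustment. But a decision taken after seeing the imbalance, with no covariate or rule named, does not replace a prespecified model.

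**Conclusion.** The point holds as a modest improvement, to be considered rather than required. Section 12.2 does not list baseline craving and leaves the outcome form, occasions and contrast open. Both planned analyses are valid under randomisation. Craving is a preliminary estimate, grouped with the secondary objectives in sections 1.2 and 12.2 and with the exploratory measures in 1.3 and 4.3, and the primary feasibility objective is untouched.

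Against a post-value analysis the trade is a loss of about 3.5 to 4% in CI width at r = 0, next to nothing at r = 0.3, and gains of about 10% and 26% at r = 0.5 and 0.7. Against a change score, adjustment gains throughout r = 0 to 0.7, least at the high end. All of this rests on 10 per arm, a single post-treatment value and an assumed r. The omission itself needs no assumption.

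**What to change.** In section 12.2, replace the choice between t-test and ANCOVA for craving with one prespecified repeated measures ANCOVA or mixed model containing treatment, visit and baseline craving on the same instrument as the outcome. State which pre-treatment value is the baseline: the screening value, as section 12.2 now defines it, or the value before session 1. Section 10.2 describes no cue procedure, so the sponsor needs to settle this for cue-elicited craving. Do not also count the chosen value as an outcome occasion.

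Apply this to the craving VAS, which the calendar marks at Baseline and before and after the TMS sessions. For the QSU-B, first reconcile section 10.5 (Baseline only) with sections 1.3, 4.3 and 12.2 (before and after each session); until then a baseline-adjusted QSU-B model cannot be specified. Keep cigarettes and sex in the craving model only if they are expected to be prognostic, since each costs a degree of freedom.

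The cost is one residual degree of freedom (18 to 17 against the t-test, 16 to 15 in the planned ANCOVA), and no gain over a post-value analysis if r is below about 0.26 to 0.28. For the VAS it takes a sentence or two and no new data. Deleting *center* is wording only: "A single study site is at the Medical University of South Carolina".

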4.3. Exploratory endpoints

Self-reported_number of cigarettes smoked per day, cue-induced craving (QSU – Brief), visual analog scale for craving and side effect will be measured pre and post each rTMS session. Other assessment, Carbon Monoxide, FTND, and MNWS-R will be completed at baseline and the last TMS. Quitting attempt will verify daily CO < 5 ppm. FTND, Feasibility metrics will also be tracked, including numbers of complete TMS sessions and dropout rate.

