6.0 Number of Subjects

The study will recruit 20 cancer patients who smoke 5 or more cigarettes per day.

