10.0 Study Design / Methods

10.1 General Design of the Study

This is a randomized, double-blinded design of active rTMS and sham rTMS. The pilot will include a total of 20 nicotine-dependent patients with cancer. Subjects will be randomized to either sham rTMS or real rTMS over the left DLPFC. At the end of 7-day study, everyone can be referred to the Hollings Cancer Center (HCC) Tobacco Treatment Program for active treatment.

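### No baseline-adjusted analysis is prespecified for the exploratory measures CO, FTND and MNWS-R, and the default two-sample test leaves their collected baseline values unused

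*Combined protocol and SAP*

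**What the plan says.** Section 4.3 lists the three measures as exploratory and fixes their timing: "Other assessment, Carbon Monoxide, FTND, and MNWS-R will be completed at baseline and the last TMS". Section 1.3 says the same.

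The analysis sentence in Section 12.2 is: "Other assessment, Carbon Monoxide, FTND, and MNWS-R will be compared between two groups". It does not say whether last-session values or changes are compared, by which test, or with which covariates. The general rule earlier in that section is: "For comparison of means (continuous variables), the two-sample t-test or the Wilcoxon rank sum test will be used as appropriate".

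Section 12.2 does name covariates (baseline daily cigarettes, sex and center). They stand in the paragraph on the secondary estimates, which covers abstinence days, cigarette consumption and cue-elicited craving. Baseline CO, FTND and MNWS-R are not among them.

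Two other places bear on the point:

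- Section 13.0, item 3 (Quality Assurance) has the first analyses check how alike the arms are at baseline, in case adjustment proves necessary. It names no outcome, covariate or threshold.
- The Section 10.5 calendar marks FTND, MNWS-R and CO at baseline only. That conflicts with Sections 1.3 and 4.3 and, for CO, with Section 10.2, item 7, which has it at each visit.

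**The concern.** In a trial of 20 patients, randomisation can easily leave the arms apart at baseline on any one measure. If last-session values are compared without regard to baseline, part of that gap carries into the estimated difference, to the extent that baseline predicts outcome. The baseline values are already to be collected, so any precision lost this way is avoidable.

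The silence on method matters too. The plan leaves open a comparison of final values, a comparison of changes, and an adjustment added once an imbalance has been seen. These can give different answers in a small trial, and nothing fixes the choice in advance.

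**Working it through.** **Inputs**

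- Total sample: "The study will recruit 20 cancer patients who smoke 5 or more cigarettes per day" (Section 6.0).
- Allocation: "Subjects will be randomized to either sham rTMS or real rTMS over the left DLPFC" (Section 10.1). No ratio is given, so I assume 1:1, 10 per arm, all with both values.
- Testing: "All statistical tests will be two-sided", at the 0.05 level (Section 12.2).
- Baseline-outcome correlation r: not given, so shown as a range.

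The plan states no power, effect size or SD for these measures, so there is no figure of its own to reproduce. Results are in SD units, taking the same SD at both times.

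**1. Chance baseline difference**

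SD of the difference in baseline means = √(2/10) = 0.447 SD.

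P(|difference| > 0.5 SD) = 2[1 − Φ(0.5/0.447)] = 0.26.

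**2. How much of it reaches an unadjusted final-value comparison**

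An imbalance of one standard error shifts the estimate by r × 0.447: 0.13 SD at r = 0.3, 0.22 SD at r = 0.5 and 0.31 SD at r = 0.7. These shifts average to zero over randomisations. They are error conditional on the imbalance that occurs, not bias.

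**3. Precision of ANCOVA against the unadjusted test**

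Variance ratio = (1 − r²)(1 + 1/(N − 4)). With N = 20 the second factor is 1 + 1/16 = 1.0625, the price of estimating one covariate.

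Interval width ratio = √(variance ratio) × t(17 df)/t(18 df) = √(variance ratio) × 2.110/2.101.

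For a change-score comparison the variance ratio is 2(1 − r).

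| r | ANCOVA variance ratio | ANCOVA interval width ratio | Equivalent unadjusted n per arm | Change-score variance ratio |
|---|---|---|---|---|
| 0 | 1.06 | 1.035 | 9.4 | 2.00 |
| 0.3 | 0.97 | 0.987 | 10.3 | 1.40 |
| 0.5 | 0.80 | 0.896 | 12.5 | 1.00 |
| 0.7 | 0.54 | 0.739 | 18.5 | 0.60 |

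A simulation of 20,000 trials at each r gave ANCOVA variance ratios of 1.06, 0.97, 0.80 and 0.54, in agreement with the formula.

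**4. Break-even**

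The variance ratio equals 1 when r² = 1 − 1/1.0625 = 0.0588, so r = 0.24. Allowing for the lost degree of freedom, the interval widths are equal at r = 0.26. Below about 0.25, adjustment costs a little precision.

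**5. Scale of the interval**

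The unadjusted 95% half-width is 2.101 × 0.447 = 0.94 SD. ANCOVA gives 0.94 × 0.896 = 0.84 SD at r = 0.5 and 0.94 × 0.739 = 0.69 SD at r = 0.7. The interval is wide either way.

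**The case against.** The strongest reply is that the plan never commits to an unadjusted test for these measures. That stands. A reader might infer that the sponsor chose one, but the sentence names no method, and the t-test or Wilcoxon reading comes from a general rule to be applied as appropriate. Section 13.0 also foresees adjustment. What remains is that the general rule is the only one supplied, and that the Section 13.0 provision would choose covariates after seeing the data.

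Second, the gain may be small in this design, and this also stands. Section 12.2 takes baseline at screening, when patients are smoking (Section 5.0 requires CO above 5 ppm). The last session falls within a quit attempt. Baseline may therefore predict outcome weakly, and CO may pile up near a floor, where linear ANCOVA fits poorly.

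Third, little rests on these measures. The primary objective is feasibility. A reader might infer that the preliminary efficacy estimates are weakened, but Sections 1.0 and 1.2 define those as abstinence days, cigarette consumption and cue-elicited craving.

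A reader might also extend the point to cigarettes per day, because Section 12.1 says the mixed models "will be used to estimate the potential treatment benefit of rTMS on numbers of cigarettes smoked per day" without naming a covariate. Section 12.2 already names baseline daily cigarettes as a covariate for cigarette consumption, so the silence in Section 12.1 is at most editorial.

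**Conclusion.** The point holds as a gap in specification. CO, FTND and MNWS-R have no stated model, the default test would leave their baseline values unused if final values are compared, and any adjustment is left to be decided from the data.

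The size depends on r. Prespecified ANCOVA would narrow the interval by about 10% at r = 0.5 and 26% at r = 0.7, change it by about 1% at 0.3, and widen it by 3.5% at r = 0. This assumes 1:1 allocation, complete data and a roughly linear relation between baseline and outcome.

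Two stronger readings are not supported. The unadjusted estimate is not biased, since over repeated randomisation it is centred on the true difference. Nor is a loss of precision certain, since it needs r above about 0.25 and the documents give no value. At r = 0.5 the residual variance falls by 25%, but the variance of the estimate falls by only 20% once the cost of estimating the covariate is counted.

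Minor priority: these are exploratory outcomes in a feasibility pilot, and no decision rule depends on them.

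**What to change.** In Section 12.2, replace the bare comparison of these measures with wording such as:

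> For each of CO, FTND and MNWS-R, the value at the last TMS session will be analysed by ANCOVA with treatment arm and the baseline value of the same measure as terms. The adjusted difference will be reported with its 95% confidence interval. A rank-based ANCOVA will be used where the outcome is strongly skewed or concentrated at a floor.

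CO is the likely case for the rank-based form. The choice should be made before the data are unblinded.

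Reconcile the Section 10.5 calendar with Sections 1.3, 4.3 and 10.2, so that it shows when each measure is taken after baseline. If the calendar is followed as it stands, there is no post-baseline value to compare.

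The cost is a few sentences and a calendar correction, with no data beyond those Sections 1.3 and 4.3 already call for. Each model spends one degree of freedom, and precision falls slightly if the correlation is below about 0.25.
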